
Rationale: H5N1 type influenza virus is a specific strain that resulted in rapid spread of influenza in birds and poultry (bird flu) across Asia, Europe and Africa. This strain has been associated with 637 human cases documented from 2003 through 2013, with a case fatality rate of 59% (WHO 2013). Widespread circulation, pathogenicity and direct transmission of avian viruses to humans suggest that H5N1 has important pandemic potential, increased by the high case fatality rate. The Sponsor is developing an adjuvanted monovalent inactivated subunit vaccine against the H5N1 strain, as the availability of a vaccine (even if incompletely matched to the pandemic virus) in the early stages of a pandemic may prevent more infections and deaths than waiting for completely matched pandemic vaccines to be produced and distributed. The production of the viral antigen components is based on cell culture technology. This production process has been used for the production of Optaflu[®] (trivalent seasonal influenza vaccine, licensed in EU, and in the US under the trade name Flucelvax[™]) and Celtura[®] (monovalent, adjuvanted, pandemic H1N1 vaccine, licensed in Germany and other countries).
 
Proprietary MF59[®] squalene-based oil-in-water emulsion adjuvant has been studied in a number of influenza vaccine formulations, and is included in a trivalent seasonal vaccine licensed for elderly adults in Europe, Flud[®], and in the registered cell culture-derived 2009 H1N1 pandemic vaccine, Celtura[®]. MF59 enhances the immune response in these seasonal and pandemic influenza vaccines and has a well-established safety profile . More than 100 million doses of MF59-adjuvanted influenza vaccines have been distributed in licensed products.
 
The MF59-adjuvanted cell culture derived H5N1 vaccine (hereafter referred to as aH5N1c) has been tested in three Phase 2 studies (V89_04, V89_13 and V89_11) in adult, elderly adult, and pediatric subjects, respectively. These studies evaluated aH5N1c in two dosage levels, 7.5 mcg + 0.25 mL MF59 (full dose) and 3.75 mcg +
		

Name of Sponsor: Seqirus, Inc.	Protocol number: V89_18	BB-IND No. 13,536

0.125 mL MF59 (half dose), in order to determine the lowest effective dose for each target population. Results from these phase 2 studies have led to the selection of the higher dose for the Phase 3 study in a healthy adult and elderly adult population.
 
The purpose of this Phase 3 study is to evaluate the safety, immunogenicity and lot-to-lot consistency of 3 lots of aH5N1c vaccine in approximately 2394 healthy adults ≥ 18 years of age receiving the vaccine. Subjects will be randomized in a 3:1 ratio to receive either aH5N1c vaccine or saline placebo. Enrollment will be stratified by age: 18 to <65 years of age and ≥ 65 years of age, to allow adequate safety assessment of the entire age spectrum. In addition, both age cohorts will be evaluated for immunogenicity according to the Center for Biologics Evaluation and Research (CBER) and the Committee for Medicinal Products for Human Use (CHMP) criteria (CBER 2007, CHMP 2003, CHMP 2006).
		

Primary Objectives
 
Co-Primary Immunogenicity Objectives:
 
To demonstrate lot-to-lot consistency across three consecutively produced lots of aH5N1c vaccine, as assessed by the ratio of geometric mean titers (GMTs) of hemagglutination inhibition (HI) antibody responses to the H5N1 vaccine strain 3 weeks after the second vaccine administration (Day 43) in healthy adult subjects ≥ 18 years of age.
 
After lot-to-lot consistency is demonstrated, the populations of all H5N1 c vaccine recipients will be pooled in order to evaluate immune responses to aH5N1c vaccine according to immunogenicity criteria defined by CBER guidance 3 weeks after the second vaccine administration (Day 43) as measured by age cohort and by strain-specific HI assay.
 
Primary Safety Objective: To evaluate the safety and tolerability of aH5N1c vaccine and placebo in healthy adult subjects ≥ 18 years of age.
 
Secondary Objectives
 
Secondary Immunogenicity Objectives: If lot-to-lot consistency is demonstrated, the populations of vaccine recipients administered aH5N1c lots will be pooled and the following objectives assessed:
 
• To evaluate immune responses to aH5N1c vaccine according to immunogenicity criteria defined by CHMP recommendations 3 weeks after the second vaccine		

Name of Sponsor: Seqirus, Inc.	Protocol number: V89_18	BB-IND No. 13,536																											

administration (Day 43) in healthy adult subjects ≥ 18 years of age by age cohort¹, as measured by strain-specific HI assay.
 
 To evaluate immune responses to aH5N1c vaccine according to immunogenicity criteria defined by CBER and CHMP recommendations 3 weeks after the first vaccine administration (Day 22) in healthy adult subjects ≥ 18 years of age by age cohort¹, as measured by strain-specific HI assay. To evaluate immune responses to aH5N1c vaccine 6 months after the first vaccine administration (Day 183) in healthy adult subjects ages ≥ 18 years of age, by age cohort, as measured by strain-specific HI assay. 																													

Methodology: This is a Phase 3 stratified, randomized, observer-blind, multi-center, placebo-controlled study to evaluate safety, lot-to-lot consistency, and immunogenicity of aH5N1c in healthy adult subjects ≥ 18 years of age. Table 1 below outlines the study design.
																													

Table 1: Study Design
 
  
 Treatment Arm	Schedule of Vaccine Administration	Total Enrolled	Enrolled by Age Group	
 
 Age 18 to <65 yrs	Age ≥ 65 yrs	
   
 Group A: aH5N1c lot #1	Day 1, Day 22	798	399	399	
 
 Group B: aH5N1c lot #2	Day 1, Day 22	798	399	399	
 
 Group C: aH5N1c lot #3	Day 1, Day 22	798	399	399	
 
 Group D: placebo	Day 1, Day 22	798	399	399	
  
			Treatment Arm	Schedule of Vaccine Administration	Total Enrolled	Enrolled by Age Group		Age 18 to <65 yrs	Age ≥ 65 yrs	Group A: aH5N1c lot #1	Day 1, Day 22	798	399	399	Group B: aH5N1c lot #2	Day 1, Day 22	798	399	399	Group C: aH5N1c lot #3	Day 1, Day 22	798	399	399	Group D: placebo	Day 1, Day 22	798	399	399
Treatment Arm	Schedule of Vaccine Administration	Total Enrolled				Enrolled by Age Group																							
			Age 18 to <65 yrs	Age ≥ 65 yrs																									
Group A: aH5N1c lot #1	Day 1, Day 22	798	399	399																									
Group B: aH5N1c lot #2	Day 1, Day 22	798	399	399																									
Group C: aH5N1c lot #3	Day 1, Day 22	798	399	399																									
Group D: placebo	Day 1, Day 22	798	399	399																									

Enrolled subjects will be age-stratified to include approximately 1596 adults 18 to <65 years of age and approximately 1596 adults ≥ 65 years of age. Subjects will be randomized in a 1:1:1:1 ratio to receive 2 doses (on Day 1 and Day 22) of either one of the three consecutively produced aH5N1c vaccine lots or placebo (Groups A, B, C, and D) according to Table 1. Approximately 1197 subjects in each age stratum will receive
																													

¹ Both CBER and CHMP criteria will be evaluated separately for each age cohort (18 to <65 years and ≥ 65 years, and 18 to <60 years and ≥ 60 years respectively).

Name of Sponsor: Seqirus, Inc.	Protocol number: V89_18	BB-IND No. 13,536

aH5N1c while 399 subjects will receive placebo. With 2394 subjects receiving active vaccine and allowing for 10% dropout, there will be approximately 2154 subjects evaluable for the primary immunogenicity objective.
 
Vaccine will be administered in an observer-blind manner. After each vaccination, subjects will remain under medical supervision at the study site for at least 30 minutes for observation of immediate adverse events (AEs). After the second vaccine administration, subjects will be monitored for approximately 6 months for antibody persistence, and approximately 12 months for safety, for a total study duration of approximately 13 months per subject.
 
The study is comprised of 17 scheduled contacts with each subject: 5 clinic visits, 4 reminder calls and 8 safety calls through a Treatment Period and a Follow-up Period:
 
• Treatment Period: Day 1 through Day 42, including 2 clinic visits and 4 reminder calls.• Follow-up Period: Day 43 through Day 387, including 3 clinic visits and 8 safety calls. 
Blood will be drawn from each subject for immunogenicity assessments before each vaccination (Day 1 and Day 22) and also on Day 43 and Day 183. Sera will be evaluated for antibody responses as measured by HI antibody responses against the H5N1 vaccine strain. Additional serologic testing methods (e.g., microneutralization (MN) testing) may be used as appropriate.
 
Lot-to-lot consistency will be analyzed based on HI immune responses in approximately 798 subjects per aH5N1c lot. All subjects will be evaluated for safety, and immunogenicity against CBER and CHMP criteria.
 
The subject diary cards will collect solicited AEs, unsolicited AEs, and medication/ vaccinations given from Day 1 to Day 7 (inclusive) and from Day 22 to Day 28 (inclusive). Unsolicited AEs, and solicited AEs that continue beyond Day 7 and 28 respectively, and medications/ vaccinations given to treat them, will be collected in the diary card until the time of return to the clinic on Day 22 and 43, respectively. In addition to these safety data, all serious adverse events (SAEs), all adverse events of special interest (AESI), new onset of chronic disease (NOCD), AEs leading to vaccine/study withdrawal, medically attended AEs, associated concomitant medications for any of these events, and all vaccinations will be collected from Day 1 through Day
		

Name of Sponsor: Seqirus, Inc.	Protocol number: V89_18	BB-IND No. 13,536

387, inclusively. These data will be captured through the subject diary card, by interview of the subject, and by review of available medical records.
 
Solicited local AEs will include: injection site induration, erythema, ecchymosis and pain. Solicited systemic AEs will include: nausea, generalized myalgia, generalized arthralgia, headache, fatigue, chills, loss of appetite, malaise and fever (derived from measured body [preferably oral] temperature ≥ 38.0 °C [≥ 100.4 °F]). Other AEs that will be measured will include body temperature and use of analgesic/antipyretic medication before and after vaccination.
 
A detailed schedule and listing of procedures is shown in Table 2, Time and Events Table, included below.
		
Number of subjects planned: Approximately 3192 healthy adults ages 18 years and older, stratified into 1596 subjects aged 18 to <65 years, and 1596 subjects aged ≥ 65 years.		
Subject Population: Healthy male and females adult subjects ≥ 18 years of age, stratified in two equal age cohorts of 18 to <65 years of age and ≥ 65 years of age.		
Subject Characteristics and Key Criteria for Inclusion and Exclusion: Subjects ≥ 18 years of age, mentally competent, in good health as determined by medical history, physical examination and clinical judgment by the Investigator; able to comply with all study procedures, to be contacted, and to be available for study visits according to the protocol. Key Exclusion Criteria are: 
- Individuals who are pregnant or breastfeeding. Female subjects of childbearing potential must have a negative pregnancy test prior to study vaccines being		

Name of Sponsor: Seqirus, Inc.	Protocol number: V89_18	BB-IND No. 13,536

administered.
 
- Females of childbearing potential² who refuse to use an acceptable method of birth control³ from Day 1 (1st vaccination) to 3 weeks after the second study vaccination, and, if sexually active, who have not used a reliable birth control method for at least two months prior to study entry.- Individuals with a body temperature ≥ 38.0 °C (≥ 100.4 °F) or any acute illness within 3 days of intended study vaccination.- Individuals who received any type of influenza vaccine (e.g., “seasonal”) within 7 days prior to enrolment in this study or who are planning to receive any type of influenza vaccine within 7 days (before or after) from the study vaccines.- Individuals who received any other licensed vaccines within 14 days (for inactivated vaccines) or 28 days (for live vaccines) prior to enrollment in this study or who are planning to receive any (non-influenza) vaccine within 28 days (before or after) from the study vaccines.- Individuals with known or suspected impairment of the immune system. 
Detailed lists of Inclusion and Exclusion Criteria are presented in Sections 4.1 and 4.2, respectively.
 
Vaccines:
 
Investigational vaccine: MF59-adjuvanted cell-culture derived subunit inactivated monovalent A/H5N1 vaccine (aH5N1c) in Pre-Filled Syringes ready for use for IM administration, containing 7.5 mcg H5N1 hemagglutinin antigen (HA) + 0.25 mL MF59 (approximately 0.5 mL total volume).
 
Control: placebo (saline solution).
		

² Female of childbearing potential is defined as a post-onset menarche and pre-menopausal female capable of becoming pregnant. This does not include females who meet any of the following conditions: (1) menopause at least 2 years earlier, (2) tubal ligation at least 1 year earlier, or (3) bilateral oophorectomy or hysterectomy.

³ Reliable birth control method is defined as sexual abstinence, hormonal (e.g., oral, injection, transdermal patch, implant, cervical ring), barrier (e.g., condom with spermicide or diaphragm with spermicide), intrauterine device (e.g., IUD), or monogamous relationship with partner who has been vasectomized for 6 months or more prior to the subject’s study entry.

Name of Sponsor: Seqirus, Inc.	Protocol number: V89_18	BB-IND No. 13,536
Immunogenicity Endpoints: The immunogenicity endpoints will be based on hemagglutinin inhibition (HI) antibody responses to the H5N1 vaccine strain. 
- GMT at Day 43 by lot- GMT at Day 1, Day 22, Day 43 and Day 183 by vaccine group (aH5N1c or placebo) and by age cohort (18 to <65 years of age and ≥65 years of age; 18 to <60 years of age and ≥60 years of age)- Percentage of subjects with HI titer ≥ 1:40 at Day 1, Day 22, Day 43 and Day 183 by vaccine group (aH5N1c or placebo) and by age cohort (18 to <65 years of age and ≥65 years of age; 18 to <60 years of age and ≥60 years of age)- Percentage of subjects achieving seroconversion (defined as: HI titer ≥1:40 for subjects negative at baseline [HI titer <1:10]; or a minimum 4-fold increase in HI titer for subjects positive at baseline [HI titer ≥1:10]) at Day 22 and Day 43 by vaccine group (aH5N1c or placebo) and by age cohort (18 to <65 years of age and ≥65 years of age; 18 to <60 years of age and ≥60 years of age)- Geometric mean ratio (GMR) at Day 1, Day 22, Day 43 and Day 183 by vaccine group (aH5N1c or placebo) and by age cohort (18 to <65 years of age and ≥65 years of age; 18 to <60 years of age and ≥60 years of age)		
Safety Endpoints: The endpoints for assessing safety and tolerability are as follows: 
- Percentages of subjects with solicited local, solicited systemic, and other adverse events as measured for 7 days following each vaccination within each vaccine group.- Percentages of subjects with unsolicited AEs reported through 21 days after last vaccination within each vaccine group.- Percentages of subjects reporting SAEs, AESIs, NOCD, AEs leading to vaccine/study withdrawal, medically attended AEs, and concomitant medications associated with these events as collected from Day 1 to Day 387 within each vaccine group.		

Name of Sponsor: Seqirus, Inc.	Protocol number: V89_18	BB-IND No. 13,536
Statistical Analysis of Primary Objectives: Co-Primary Immunogenicity Objectives: The lot-to-lot consistency will be claimed if the two-sided 95% confidence intervals (CIs) of all the three pairwise comparisons (GMT(Group A)/ GMT(Group B), GMT(Group A)/ GMT(Group C), GMT(Group C)/ GMT(Group B)) fall within 0.667 and 1.5. Significance level to all these tests is $\alpha = 5\%$, which needs no adjustment for multiplicity as all hypotheses have to be rejected (intersection-union test problem). With the proposed sample size, assuming a standard deviation of 0.85 for the log ₁₀ antibody titers (for each vaccine lot), approximate pairwise equivalence of factor 1 and independency, a single equivalence test based on 718 subjects per lot group has a power of 95%. The resulting overall power is approximately 86%, because the total number of comparisons is three. To account for dropouts (approximately 10%), a total of n=798 per lot should be recruited. After demonstrating success of the lot-to-lot consistency, the achievement of the CBER criteria (co-primary objective) will be claimed if the lower bound of the two-sided 95% CI for the percent of subjects achieving an HI antibody titer $\geq 1:40$ should meet or exceed 70% or 60% (for subjects 18 - <65 years of age and subjects ≥ 65 years of age, respectively) for all lots pooled. With the proposed sample size of 1077 per age cohort and the assumed proportions based on previous studies, such as V89_04 and V89_13 the power to meet or exceed 70% or 60% of the subjects achieving an HI antibody titer $\geq 1:40$ is 82% - > 99% (based on the age cohort). Primary Safety Objective: There is no statistical null hypothesis associated with the safety objective, which will be analyzed descriptively.		
Planned Analyses: An interim analysis of immunogenicity will be performed for all subjects through the Day 43 visit. Site staff and Sponsor personnel involved in study conduct will remain blinded to treatment assignments for this interim analysis. The final analysis will be performed when all data up to the study end (Day 387) are available. Analysis will be done on fully unblinded data set by the Sponsor and all data will be presented in the final study report.		
Data Monitoring Committee: No Data Monitoring Committee (DMC) is planned in		

Name of Sponsor: Seqirus, Inc.	Protocol number: V89_18	BB-IND No. 13,536
this study.		

Table 2: Times and Events Table, Scheduled Subject Contacts 1 – 17

Study Periods	Treatment Period						Follow-up Period										
Visit Number (V); Reminder Call (RC) Safety Call (SC); Study Day (D)	V1 D1	RC D3	RC D5	V2 D22	RC D24	RC D26	V3 D43	V4 SC D91	V5 SC D122	V6 SC D152	V7 D183	V8 SC D217	V9 SC D251	V10 SC D285	V11 SC D319	V12 SC D353	V13 D387
Visit Window	Day -5 to Day 1	2-3 days post 1st vac	4-5 days post 1st vac	21-30 days post 1st vac	2-3 days post 2nd vac	4-5 days post 2nd vac	21-30 days post 2nd vac	90 – 100 days post 1st vac	121-131 days post 1st vac	151-161 days post 1st vac	182 – 192 days post 1st vac	216- 225 days post 1st vac	250- 259 days post 1st vac	284-293days post 1st vac	318-327 days post 1st vac	352-361 days post 1st vac	386-395 days post 1st vac
Informed Consent ^a	X																
Medical history ^b	X																
Review of systems ^b	X			X			X				X						X
General physical examination ^b	X																
Symptom-directed physical examination ^b				X			X				X						X
Pregnancy test ^c (Women of childbearing potential)	X			X			X										
Measurement of body temperature (preferably oral) ^d	X			X													
Exclusion/Inclusion criteria ^e	X																
Enrollment and randomization ^f	X																

Study Periods	Treatment Period						Follow-up Period										
	V1 D1	RC D3	RC D5	V2 D22	RC D24	RC D26	V3 D43	V4 SC D91	V5 SC D122	V6 SC D152	V7 D183	V8 SC D217	V9 SC D251	V10 SC D285	V11 SC D319	V12 SC D353	V13 D387
Visit Window	Day -5 to Day 1	2-3 days post 1st vac	4-5 days post 1st vac	21-30 days post 1st vac	2-3 days post 2nd vac	4-5 days post 2nd vac	21-30 days post 2nd vac	90 – 100 days post 1st vac	121-131 days post 1st vac	151-161 days post 1st vac	182 – 192 days post 1st vac	216- 225 days post 1st vac	250- 259 days post 1st vac	284-293days post 1st vac	318-327 days post 1st vac	352-361 days post 1st vac	386-395 days post 1st vac
Serology blood draw (max: 12 mL whole blood) ^g	X			X			X				X						
Review criteria for repeat vaccination ^h				X													
Study vaccine administered ⁱ	X			X													
30 minute post-injection adverse event assessment ^j	X			X													
Diary card dispensed (and training on completion) ^j	X			X													
Diary card reminder call ^k		X	X		X	X											
Diary card reviewed and collected ^l				X			X										
Assess all AEs ^m	X			X			X										
Assess local and systemic solicited AEs ^l				X			X										

Study Periods	Treatment Period						Follow-up Period										
Visit Number (V); Reminder Call (RC) Safety Call (SC); Study Day (D)	V1 D1	RC D3	RC D5	V2 D22	RC D24	RC D26	V3 D43	V4 SC D91	V5 SC D122	V6 SC D152	V7 D183	V8 SC D217	V9 SC D251	V10 SC D285	V11 SC D319	V12 SC D353	V13 D387
Visit Window	Day -5 to Day 1	2-3 days post 1st vac	4-5 days post 1st vac	21-30 days post 1st vac	2-3 days post 2nd vac	4-5 days post 2nd vac	21-30 days post 2nd vac	90 – 100 days post 1st vac	121-131 days post 1st vac	151-161 days post 1st vac	182 – 192 days post 1st vac	216- 225 days post 1st vac	250- 259 days post 1st vac	284-293days post 1st vac	318-327 days post 1st vac	352-361 days post 1st vac	386-395 days post 1st vac
Assess SAEs, AESIs, medically attended AEs, AEs leading to withdrawal, and NOCD ^m	X			X			X	X	X	X	X	X	X	X	X	X	X
Assess relevant medications ⁿ	X			X			X	X	X	X	X	X	X	X	X	X	X
Study Termination ^o																	X
Footnotes:																	
a. See sections 3.2.1 and 12.2			d. See sections 3.2.5.1 and 4.3			j. See section 3.2.5.3											
b. See section 6.2			e. See sections 4.1 and 4.2			k. See section 3.2.5.4											
c. See section 3.5			f. See sections 3.2.3 and 3.2.4			l. See section 3.4.1											
			g. See sections 3.1 and 3.6			m. See sections 6.6.1, 6.6.1.1, 6.6.2 and 6.6.3											
			h. See sections 4.1, 4.2 and 4.4			n. See section 5.4											
			i. See sections 3.2.5.2, 5.1 and 5.3			o. See section 3.2.5.8											

TABLE OF CONTENTS

PROTOCOL SYNOPSIS V89_18 VERSION 3.0	2
TABLE OF CONTENTS.....	14
LIST OF ABBREVIATIONS.....	18
1.0 BACKGROUND AND RATIONALE	19
2.0 OBJECTIVES.....	23
2.1 Primary Objectives	23
2.2 Secondary Objectives	23
3.0 STUDY DESIGN AND INVESTIGATIONAL PLAN.....	25
3.1 Overview of Study Design.....	25
3.1.1 Study Period	27
3.2 Study Visit Procedures	27
3.2.1 Informed Consent	27
3.2.2 Screening Procedures.....	27
3.2.3 Enrollment	28
3.2.4 Randomization.....	28
3.2.5 Visit Procedures.....	29
3.3 Blinding Procedures.....	34
3.4 Data Collection	35
3.4.1 Data collected from subjects.....	35
3.4.2 Electronic and Paper Case report forms	35
3.5 Pregnancy Testing	36
3.6 Laboratory Assessments	36
3.6.1 Processing, Labeling and Storage of Serum Samples for Serology	36
3.6.2 Safety Laboratory Assessments.....	36
3.6.3 Cell Mediated Immunity Assessments	36
3.6.4 Culture/PCR/Genotyping Assessments	36
3.7 Stopping/Pausing Guidelines.....	37
3.8 Premature Withdrawal and Early Study Termination.....	37

3.9	Early Termination Visit	39
4.0	SELECTION OF STUDY POPULATION.....	41

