7.2 Success Criteria

7.2.1 Success Criteria for Co-Primary Objectives

Lot-to-lot consistency, derived from Day 43 HI titers for each aH5N1c lot, will be claimed if, for subjects ≥ 18 years of age in the Per Protocol Set, the two-sided 95% confidence intervals (CIs) of all the three pairwise comparisons (GMT(Group A)/ GMT(Group B), GMT(Group A)/ GMT(Group C), GMT(Group C)/ GMT(Group B)) fall within 0.667 and 1.5. Significance level to all these tests is $\alpha = 5\%$, which needs no adjustment for multiplicity as all hypotheses have to be rejected (intersection-union test problem).

Furthermore after lot-to-lot consistency is achieved, CBER criteria for the percentage of subjects with HI titer $\geq 1:40$ on Day 43 will be assessed as below, for subjects from both age cohorts (18 to 65 years of age and ≥ 65 years of age) on pooled lots. The overall power to fulfill those CBER criteria is 98%.

Immunogenicity according to CBER in subjects 18 - < 65 years of age

The aH5N1c vaccines immunogenicity will be evaluated in subjects 18 to < 65 years of age, using the following measurements according to the current CBER criteria for the adult population (CBER 2007):

- The lower bound of the adjusted two-sided 95% CI for the percentage of subjects achieving an HI antibody titer $\geq 1:40$ should meet or exceed 70%.

Immunogenicity according to CBER in subjects ≥ 65 years of age

The aH5N1c vaccine immunogenicity will be evaluated in subjects ≥ 65 years of age, using the following measurements according to the current CBER criteria for the ≥ 65 years of age population (CBER 2007):

- The lower bound of the adjusted two-sided 95% CI for the percentage of subjects achieving an HI antibody titer $\geq 1:40$ should meet or exceed 60%.

The study will be considered a success if both lot-to-lot consistency for subjects aged ≥ 18 years, and CBER criteria (titer above 1:40) for both age cohorts (18-65 years and ≥ 65 years) are met.

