7.4.2.2 Statistical Methods for Co-Primary Objectives

Log-normal distributed data

All statistical analyses for HI will be performed on the logarithmically (base 10) transformed values. Individual HI titers below detection limit will be set to half that limit.

Geometric mean HI antibody titers (GMT)

Adjusted estimates of geometric mean titers (GMTs), and their associated 95% CIs at Day 43 will be determined using analysis of covariance (ANCOVA) with factors for lot, age groups (18-64, ≥ 65), center and a covariate for the effect defined by the log-transformed prevaccination antibody titer. Influenza-antibody GMTs (Day 43), associated two-sided 95% CIs and median, minimal, and maximal area/titer values will be determined and presented together with N (number of subjects), by lot (for the first primary objective) . This model will include only immunogenic data from the 3 lots of aH5N1.

Statistical analyses will be performed on the logarithmically (base 10) transformed titer values, while median, minimum, and maximum values will be obtained on the actual titer values.

To assess equivalence of lots, the limit of the 95% CI will be compared with the pre-specified thresholds (see [Section 7.2.1](#)).

Analysis of binary data

Binary data (proportion of subjects with HI titer $\geq 1:40$) will be analyzed using loglinear models with a factor for dose group adjusted for center, at Day 43. Proportions and two-sided 95% CIs will be calculated based on these models. Models might be simplified in case of convergence problems.

Handling of missing values for Immunogenicity Data

For immunogenicity data, it may be reasonable to consider missing immunogenicity values as missing completely at random (MCAR), i.e., not informative. Therefore, the primary analysis will comprise a complete case analysis only, without introducing any bias. Imputation methods will not be used.

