7.4.2.3 Sample Size and Power Considerations of Co-Primary Objectives

Data observed in previous studies in similar sets (V89_04 in subjects 18-64 years of age; V89_13 in subjects > 65 years of age) showed a variability of the post vaccination titers ranging from 0.75 to 0.88 (in the log scale). With the proposed sample size, assuming a standard deviation of 0.85 for the log₁₀ antibody titers (for each vaccine lot), approximate pairwise equivalence of factor 1 and independency, a single equivalence test based on 718 subjects per lot group has a power of 95%. The resulting overall power is approximately 86%, because the total number of comparisons is three. To account for dropouts (approximately 10%), a total of $n=798$ per lot should be recruited.

Data observed in previous studies in similar populations (V89_04 in subjects 18- <65 years of age; V89_13 in subjects > 65 years of age) showed a proportion of 86% of subjects aged 18 to <65 years and a proportion of 81% of subjects aged 65 years and older achieving an HI antibody titer of $\geq 1:40$. With a sample size of 1077 evaluable subjects from the pooled lots there is an overall power of approximately 98% to achieve the CBER criteria (HI antibody titer $\geq 1:40$ for at least 70% of the subjects aged 18 to <65 years, and for at least 60% of the subjects aged 65 years and older). To account for dropouts (approximately 10%), a minimum sample size of $n=1197$ for all lots combined are needed.

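### The 82% lower end of the CBER power range in the synopsis follows from no planning rate the protocol states, and at those rates it contradicts the 98% overall power in 7.2.1 and 7.4.2.3

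*Protocol*

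**What the plan says.** The synopsis (Statistical Analysis of Primary Objectives) makes the CBER test conditional on the lot result: "After demonstrating success of the lot-to-lot consistency, the achievement of the CBER criteria (co-primary objective) will be claimed" if the lower limit of the two-sided 95% CI reaches 70% (18 to <65 years) or 60% (≥65 years), lots pooled. With 1077 subjects per cohort and "assumed proportions based on previous studies, such as V89_04 and V89_13", it says the power "is 82% - > 99% (based on the age cohort"). The rates themselves are not given in the synopsis.

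Section 7.4.2.3 gives them. The same two studies "showed a proportion of 86% of subjects aged 18 to <65 years and a proportion of 81% of subjects aged 65 years and older" with a titer of at least 1:40. With 1077 evaluable subjects, "there is an overall power of approximately 98% to achieve the CBER criteria". Section 7.2.1 repeats this ("The overall power to fulfill those CBER criteria is 98" per cent) and makes study success depend on lot consistency and on the "CBER criteria (titer above 1:40) for both age cohorts".

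SAP Appendix 20.1 (the sample size memo) shows power 99 at n=1077 for each cohort, by a normal approximation at two-sided 0.05. SAP Appendix 20.2 (the review of that memo) shows power >.999 for each cohort, by an exact binomial calculation at one-sided 0.05.

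**The concern.** Two parts of the same protocol give different power for one co-primary objective. The synopsis allows up to an 18% chance of missing the criterion in one cohort (1 − 0.82). Sections 7.2.1 and 7.4.2.3 allow 2% for both cohorts together (1 − 0.98). Success in both cohorts is required, so the two statements cannot be true on the same assumptions.

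The synopsis figure also cannot be checked. It refers to earlier studies without giving their rates, and the rates given for those studies elsewhere do not produce it. A reader who relies on the synopsis gets a risk for a study-deciding criterion that the sponsor's own calculations contradict.

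**Working it through.** **Inputs.** n = 1077 evaluable per cohort (synopsis; 7.4.2.3). Thresholds p0 = 0.70 and 0.60 (synopsis; 7.4.2). Planning rates p1 = 0.86 and 0.81 (7.4.2.3; SAP Appendix 20.1). The success rule is the lower limit of a two-sided 95% CI, which is a one-sided test at 0.025.

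**Reproducing the sponsor's calculations.** For the exact binomial test, find the smallest count c with P(X ≥ c | n, p0) ≤ α. Power is then P(X ≥ c | n, p1). At one-sided 0.05 this gives:

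- 18 to <65 years: c = 780, actual α 0.0435, power >.999.
- ≥65 years: c = 674, actual α 0.0444, power >.999.

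Both match SAP Appendix 20.2. The memo's 99 per cohort gives 0.99 × 0.99 = 0.980, which equals the 98% in 7.2.1 and 7.4.2.3. The 82% appears in neither calculation.

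**Power under the actual decision rule (one-sided 0.025).**

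| Cohort | p1 vs p0 | c | Actual α | Power |
|---|---|---|---|---|
| 18 to <65 | 0.86 vs 0.70 | 784 | 0.0238 | >99.9% |
| ≥65 | 0.81 vs 0.60 | 679 | 0.0219 | >99.9% |

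The memo's normal approximation agrees. Power = Φ(z), with z = [|p1 − p0|√n − 1.96√(p0(1 − p0))] / √(p1(1 − p1)):

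- 18 to <65: (0.16 × 32.82 − 1.96 × 0.458) / 0.347 ≈ 12.5.
- ≥65: (0.21 × 32.82 − 1.96 × 0.490) / 0.392 ≈ 15.1.

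**Could another reading give 82%?**

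- *Lower rate against the higher threshold* (81% vs 70%, n = 1077): still >99.9%.
- *One lot within one cohort* (n = 359): >99.9% at each cohort's own rate.
- *A smaller evaluable n*: exact power is saw-toothed in n. It crosses 82% between about n = 57 and 66 (86% vs 70%) and between about 42 and 45 (81% vs 60%).
- *Center adjustment*: the planned analysis is not a plain binomial, because these data "will be analyzed using loglinear models with a factor for dose group adjusted for center, at Day 43". To bring power down to 82%, the adjustment would have to cut the effective sample size about 16-fold (1077/66) to 26-fold (1077/42), which is not plausible.
- *Including the lot-consistency test*: 0.86 × 0.98 = 0.843. That is not 82%, and it is not a cohort-level figure.
- *A different planning rate*: at n = 1077 and one-sided 0.025, 82% power needs a true rate of 74.0% (threshold 70%), which is 12.0 points below 86%, or 64.3% (threshold 60%), which is 16.7 points below 81%. Neither rate is stated.

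**Compatibility with 98%.** P(both cohorts succeed) ≤ min(power in cohort 1, power in cohort 2). If one cohort has 82%, overall power is at most 82%. With 99% in the other cohort it is 0.82 × 0.99 = 0.81. Either way it is at least 16 points below the stated 98%. This bound holds for any choice of test.

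**The case against.** The arithmetic is not in dispute. Three points can be made in the sponsor's defence.

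First, the synopsis cites its source studies only as examples and prints no rates, so 82% may reflect a deliberately cautious rate. A true rate of exactly 74% against the 70% threshold gives 82.6% exact power, and a round number landing so close would fit such a case. This stands as a possibility. It explains the figure only by supposing a rate that no document gives, and it would still mean that the 98% rests on different assumptions. The documents do not show whether 82% is a leftover or a deliberate lower-rate case, so the fix must allow for both.

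Second, nothing operative depends on the figure. SAP section 5 sends the reader to protocol 7.4.2.3 and Appendix A, which agree with 7.2.1 and with each other. Enrolment, the decision rule and the interim analysis are unaffected. This is correct and it limits the consequence. It does not make the synopsis statement right, because that statement concerns a criterion on which study success depends.

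Third, the recalculated power comes from an unadjusted binomial model, while the planned model adjusts for center. That is a reason to report >99.9% and no finer figure. It does not bridge the gap to 82%.

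**Conclusion.** The concern holds. At the only rates the documents state (86% and 81%), with 1077 evaluable subjects per cohort and the two-sided 95% CI rule, power is above 99.9% in each cohort, against a synopsis lower end of 82%. On the same assumptions, 82% in either cohort also excludes the 98% overall power in 7.2.1 and 7.4.2.3, a gap of 16 points.

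The recalculation assumes a binomial model without center adjustment and takes the CBER test as conditional on lot consistency. The conflict with 98% needs only that both figures rest on the same assumptions.

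The 82% understates power at the stated rates. The objective is not underpowered, and the 98% is conservative. What is wrong is the power statement in the synopsis, and it should be corrected.

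**What to change.** Change the one sentence in the protocol synopsis. The sponsor knows which option applies.

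- **(a) If 82% has no current basis**, replace the range with: *>99% in each age cohort and at least 98% overall, conditional on lot-to-lot consistency (1077 evaluable per cohort, assumed rates 86% and 81%, two-sided 95% CI, unadjusted binomial calculation)*.
- **(b) If 82% is a deliberate lower-rate case**, state the rate, the cohort it applies to and its source, label it a sensitivity case, and say that the 98% overall power does not apply to it.

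The cost is one sentence. Sections 7.2.1 and 7.4.2.3, the SAP and its dated sample size memo, the sample size, the decision rule and the analysis all stay as they are.
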